3. IDENTIFICATION AND DESCRIPTION OF THE INVESTIGATIONAL DEVICE

SPINERY is an active medical device intended for radiofrequency thermal ablation of metastatic bone tumors. SPINERY is a class IIb medical device as per rule 9 of Medical Device Regulation, annex VIII.

It is mainly composed by

- RF generator (Figure 1) for parameter control and treatment modulation; equipped with a peristaltic pump intended to allow the flow of cooling fluid inside RF electrode needles during ablation procedure. Footswitch is provided together with the generator.

Figure 1- SPINERY RF Generator

RF needle device composed by a handle with electrode needle (monopolar or bipolar) available in the following variants in order to offer an adequate treatment for many tumor shapes and dimensions:

- Monopolar needle 13 mm with irrigation and cooling, code SP-MI13
- Bipolar needle 7x4x7 mm with irrigation and cooling, code SP-BI0704
- Bipolar needle 10x5x10 mm with irrigation and cooling, code SP-BI1005

The 3 available variants (codes SP-MI13, SP-BI0704, SP-BI1005) consist of cooled needles capable of providing irrigation of tissue during ablation procedure. The needle is hollow and its inner space is divided into 3 concentric lumens:

- The inner central lumen is used to distally deliver the irrigation solution to the tip of the RF needle; a hole on the needle tip allows the irrigation solution to reach tissues (the irrigation solution could be also delivered proximally through the insulation and irrigation cannula);
- The intermediate lumen is used to deliver a cooling fluid towards the proximal thermocouple;
- The outer external lumen returns the cooling fluid from the proximal thermocouple towards the cooling tubing circuit connected to the handle of the RF needle device; the cooling fluid is not intended to come in contact with patient tissues because it flows in a closed circuit.

[figure not shown]
The 3 needle variants SP-MI13, SP-BI0704 and SP-BI1005 also contain two thermocouples (distal thermocouple inside the ablation area and proximal thermocouple at the edge of ablation area) that permit

real-time monitoring of temperatures at the center of the ablation zone and at the edge of ablation area ensuring that no healthy tissue around tumor is damaged.

Figure 2 - SPINERY Cooled Bipolar Needle

The expected dimensions of the RF ablation areas, obtained with SPINERY system during in-vivo sessions treating healthy vertebral bodies, are below summarized (see also IFU):

Needle code	Type of ablation *	Electrode/s lenght	Distal thermocouple temperature Td**	Proximal thermocouple temperature range Tp***	Expected ablation dimensions L1xL2xL3****	Expected ablation area size	Expected ablation volume size	Power range****	Total ablation time
SP-BI0704		7 mm (intra-electrodes distance of 4 mm)	90°C	31-44°C	17 x 10 x 10 mm	134 mm ²	890 mm ³	6-15 W	6:00 min
SP-BI1005		10 mm (intra-electrodes distance of 5 mm)	90°C	31-44°C	22 x 12 x 12 mm	207 mm ²	1.658 mm ³	6-15 W	6:00 min
SP-MI13 + Neutral plate		13 mm	90°C	31-44°C	15 x 8 x 8 mm	94 mm ²	503 mm ³	6-15 W	6:00 min

(*) Type of expected ablation based on in-vivo test data. The experimental animal model should be considered informative but not prescriptive in the sizing of the target volumes, as these are healthy and non-metastatic biological tissues, the bone tissue is homogeneous and confined within the bone theca of the cortical bone of the vertebra.

(**) All the ablation parameters shown in the table refer to the target ablation temperature of 90 ° C detected by the distal thermocouple Td (ablation ramp that provides 3 levels of heating).

(***) Temperature range of the proximal thermocouple detected upon reaching the target ablation temperature of 90°C (detected by Td).

(****) Expected ablation dimensions that also include the portion of tissue called the transition crown of ablation, which is about 2-3 mm.

For the calculation of the ablation volume it is assumed that the size of L3 is equal to the size of L2.

(*****) Power range automatically delivered by the generator during the target temperature maintenance period of 90°C (2 minutes)

NOTES:

- The ablation area and volumes in a bipolar or monopolar double needle configuration are strongly influenced by the relative distance between the electrodes.
- The ablation area in a double bipolar crossed needle configuration may have a different geometric shape from the ellipse. It can switch from partially overlapping double ellipsoids (distant electrodes) to a more rounded ablation area (nearby electrodes) depending on the relative distance between the electrodes.

Table 1 - SPINERY system expected ablation dimensions

Accessories that can be described as follows:

- Connection cooling tubing to connect the handle with the cooling solution, code SP-CS and code SP-CD;
- Bone access accessories:
- Drill;
- Diamond tip trocar;
- Oblique tip trocar;
- Introducer;
- Insulation and irrigation cannula;
- Syringe to inject irrigating solution through the needle lumen or through insulation and irrigation cannula;
- Footswitch;
- Connection for neutral plates;

Figure 3 - SPINERY RF system and accessories

4. OBJECTIVES

SPINERY is a Radio-Frequency (RF) device designed for the pain reduction in patients with metastatic bone tumors. In particular, SPINERY is intended for:

- Pain reduction in patients affected by metastatic bone tumors involving the vertebral bodies, sacrum, iliac crest and peri-acetabulum, in patients with indication for Standard Therapy and in patients who have failed, not candidates or refuse Standard Therapy;
- Coagulation and ablation of bone tissue during interventional procedures including palliation of pain associated with metastatic lesions involving bone also in patients with indication for Standard Therapy and in patients who have failed, not candidates or refuse Standard Therapy.

The main objective of this pre-marketing study is to demonstrate the safety and efficacy of SPINERY RF device in the palliative treatment of patients with metastatic bone tumors in the areas of vertebral bodies (thoracic and/or lumbar), sacrum, iliac crest and peri-acetabulum and to prove the conformity of this device with the Essential Requirements for CE-marking [Medical Device Regulation 2017/745].

4.1. Primary Objectives

- To demonstrate that SPINERY RF device is effective in short-term (3 months) pain reduction in patients affected by metastatic bone tumors involving the vertebral bodies, sacrum, iliac crest and peri-acetabulum with indications for standard therapy in patients who have failed, not candidates or refuse standard therapy;
- To demonstrate that SPINERY RF device is safe in the RF ablation treatment of metastatic bone tumors, without causing device-related adverse events including in particular nerve injury;

4.2. Secondary Objectives

- To demonstrate that SPINERY RF device is effective in long-term (12 months) pain reduction in patients affected by metastatic bone tumors in the areas of vertebral bodies (thoracic and/or lumbar), sacrum, iliac crest and peri-acetabulum.
- To demonstrate safety in relation to usability;
- To demonstrate the procedural performance in terms of a short learning curve.

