Objective(s), primary and secondary	
Primary objectives:
 
 1. To demonstrate that SPINERY RF device is effective in short-term (3 months) pain reduction in patients affected by metastatic bone tumors involving the vertebral bodies, sacrum, iliac crest and peri-acetabulum with indication for standard therapy and in patients who have failed, not candidates or refuse standard therapy; 2. To demonstrate that SPINERY RF device is safe in the RF ablation treatment of metastatic bone tumors, without causing device-related adverse events including, in particular, nerve injury; 
Secondary objectives:
 
 1. To demonstrate that SPINERY RF device is effective in long-term (up to 12 months) pain reduction in patients affected by metastatic bone tumors in the areas of vertebral bodies (thoracic and/or lumbar), sacrum, iliac crest and peri-acetabulum; 2. To demonstrate safety in relation to usability; 3. To demonstrate the procedural performance in terms of a short learning curve.
Hypotheses, primary and secondary	
Primary hypothesis:
 
 - BPI Brief Pain Inventory scale performance in terms of palliative treatment: 
H0: $\mu_c = 0$
 
HA: $\mu_c \neq 0$
 
Where μ_c is the mean change from baseline to the 3-month visit in worst-pain score.
 
No formal hypotheses for the remaining objectives.

Risks and anticipated adverse device effects to be assessed	Risks of innovative device SPINERY are the same of the state-of-the-art technology: 
 - Carbonization - Post-operative pain

	
 - Limited/uncomplete treatment due to anatomical peculiarities - damage to surrounding tissue through iatrogenic injury - Nerve injury including thermal injury, puncture of spinal cord or nerve roots potentially resulting in radiculopathy, paresis, and paralysis - Pulmonary embolism - Hemothorax or pneumothorax - Infection - Unintended puncture - Hemorrhage - Hematoma
Design of the clinical investigation	
Clinical development stage	
Pivotal confirmatory.
 
Justification: pre-market study for demonstration of conformity of the device with the Essential Requirements for CE-marking.

Design type	Prospective, Single arm, Multicenter
Control group	No control group

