5.2. Secondary Endpoints

- Change of Worst Pain Score: Thoracic/Lumbar/ Peri-acetabulum/Iliac Crest/Sacrum RF Ablation [Time Frame: Baseline vs. 1 month and 12 months];

Worst pain score at the target treatment site will be collected from the Brief Pain Inventory (BPI) in the past 24 hours.

- Usability endpoint: Technical success (ability to perform access to treatment site and perform ablation) and procedural success (ability to perform access to treatment site and perform ablation for one or more complete cycles as planned by the physician) without product specialist intervention [Timeframe: Post-procedure];
- Short learning curve endpoint: procedure time, number of procedural errors, number of procedural and technical success for the same surgeon [Time Frame: Post-procedure];

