6.5.2. Withdrawal of Participants from Study Treatment

Each participant has the right to withdraw from the study at any time. In addition, the investigator may discontinue a participant from the study at any time if the investigator considers it necessary for any reason including:

- Pregnancy

- Ineligibility (either arising during the study or retrospective having been overlooked at screening)
- Significant protocol deviation
- Significant non-compliance with study requirements
- An adverse event which requires treatment discontinuation, such as adverse events related to complications during anesthesia procedure performed before RF ablation treatment, leading to the impossibility to treat the subject with SPINERY (for example inability of the patient to tolerate required level of anesthesia)
- An adverse event which results in inability to continue to comply with study procedures, that is any adverse event, which is related or not to SPINERY device and impedes the subject from attending to scheduled follow-up visits
- Disease progression which results in inability to continue to comply with study procedures, because it requires reintervention through ablation or other treatments in order to stop the progression; possible reintervention might not allow to conclude study procedures and might confound results interpretation
- Need for a second ablation procedure with SPINERY RF device or other similar devices, as per clinical judgment
- Consent withdrawn
- Lost to follow up

If a participant is withdrawn due to an AE/SAE, every attempt will be made by the investigator to obtain follow-up information about the AE/SAE until resolution or a determination that the AE/SAE will not be resolved.

If the participant withdraws consent for disclosure of future information, the sponsor may retain and continue to use any data collected before such a withdrawal of consent.

If a participant withdraws from the study, he/she may request destruction of any samples taken and not tested, and the investigator must document this in the site study records.

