10.2. Number of Participants

Approximately 52 patients will be enrolled in the study.

A sample size of 36 successfully treated subjects who complete the 3-months period of follow-up will allow to detect a difference between the pre-treatment and post-treatment means of worst pain score collected from the BPI equal to 2 points (e.g., from 7 to 5 points), assuming that the SD of the scores is equal to 3 and the correlation between measurements at different time periods is 0.3, and with two-tailed alpha = 0.05 and study power of 0.90. Such a 2-points difference is considered as the minimally important difference for the worst pain rating of the BPI (Corli O et al, 2010: p.51; *Misurare il dolore nel paziente con cancro nella ricerca e nella clinica*; Mathias SD et al, 2011; 9:72-78; J Support Oncol). Taking into account about 30% of patients' attrition from treatment through the pain assessment at 3 months, 52 subjects will be enrolled in the study. Sample size calculation was performed using the “proc power” in SAS v.9.4 software (Cary, NC, USA).

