10.4. Clinical Study Reports

Clinical study reports will be issued at the completion of the following timeframes on all patients:

- Postoperative, at achievement of primary safety endpoint;
- 1 month, at achievement of the first timeframe of the secondary endpoint concerning the change of worst pain score;
- 3 months (the primary endpoint) for CE mark purposes, at achievement of primary efficacy endpoint;
- 12 months at achievement of the second timeframe of the secondary endpoint concerning the change of worst pain score (Final Clinical Report);

Statistical analysis will be performed at 1-month, 3-months and 12-months intervals on BPI worst pain score results and change as compared to baseline values.

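### The 12-month objective is worded as a demonstration, but the plan supports only a mean in selected completers, with no rule for death, withdrawal or repeat ablation

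*Combined protocol and SAP*

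**What the plan says.** Section 4.2 lists, as a secondary objective to be demonstrated, that the device is "effective in long-term (12 months) pain reduction". The synopsis has the same objective, extended up to 12 months. Section 5.2 measures it by change in BPI worst pain, with the time frame "Baseline vs. 1 month and 12 months".

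The analysis is covered by one sentence in section 10.4: "Statistical analysis will be performed at 1-month, 3-months and 12-months intervals on BPI worst pain score results and change as compared to baseline values". The synopsis adds: "No formal hypotheses for the remaining objectives". Section 10.1 names ITT for all analyses and PPT as secondary, but defines neither set. No section says what happens to the 12-month result when a patient dies, withdraws, is re-treated or misses the visit.

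Section 6.5.2 lists reasons for which the investigator may discontinue a participant from the study. They include disease progression that prevents compliance because reintervention is required, and "Need for a second ablation procedure with SPINERY RF device or other similar devices, as per clinical judgment".

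The only attrition figure is in section 10.2: about 30%, described as "attrition from treatment through the pain assessment at 3 months". No retention or survival figure is given for month 12.

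**The concern.** A change score exists only for a patient with a 12-month score. In a metastatic population with Karnofsky 40 or more at entry, some patients will die before then. Others may be discontinued because the disease progressed or the site needed a second ablation, and the latter may well be a local failure of the first. Both routes can remove poor outcomes from the 12-month mean. Calling the analysis ITT does not change this, because the label supplies no value for a patient without a score. A rule for missing 3-month scores would not settle it either, since death and re-treatment need a rule of their own.

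At stake is the 12-month Final Clinical Report. It has an objective worded as a demonstration, no hypothesis to test it against, and a mean taken in whoever remains. A drop in that mean could be read as sustained benefit when part of it comes from who was left to measure.

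**Working it through.** **1. The plan's own figure (section 10.2).** Inputs: SD 3, correlation 0.3, difference 2 points, two-sided alpha 0.05, power 0.90, attrition about 30%.

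- SD of change = sqrt(2 × 3² × (1 − 0.3)) = sqrt(12.6) = 3.55.
- Paired t-test, noncentral t: n = 35 gives power 0.899 and n = 36 gives 0.908, so 36 is reproduced.
- Enrolment: 36 / 0.70 = 51.4, rounded up to 52. Reproduced.

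**2. How many might remain at 12 months.** The documents do not say. Assumption: a further fraction q is lost in each of the three 3-month periods after month 3. Retained share = 0.70 × (1 − q)³. Half-width of the 95% CI = t(0.975, n − 1) × 3.55 / sqrt(n).

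| q (assumed) | Share retained | Patients of 52 | 95% CI half-width |
|---|---|---|---|
| 0% | 70% | 36 | 1.2 points |
| 5% | 60% | 31 | 1.3 |
| 10% | 51% | 26 to 27 | 1.4 |
| 20% | 36% | 19 | 1.7 |
| 30% | 24% | 12 | 2.3 |
| 40% | 15% | 8 | 3.0 |

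For the 30% row: 0.70⁴ = 0.240; × 52 = 12.5; with n = 12, 2.201 × 3.55 / sqrt(12) = 2.3.

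**3. How far selection could move the mean.** Assumptions, none from the documents: change is normal with true mean 0 and SD 3.55, and a patient whose change is z SDs worse than average has a hazard of loss multiplied by exp(b × z), with b = 0.2 or 0.4. The baseline cumulative hazard H is set so that 70% remain at 3 months. If the cumulative hazard at 12 months is k × H, the probability of remaining is S(z) = exp(−k × H × exp(b × z)), and the completer mean is 3.55 × E[z S(z)] / E[S(z)]. The calibrated H is 0.352 for b = 0.2 and 0.339 for b = 0.4.

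| Loss after month 3 | Retained | Completer mean, b = 0.2 | Completer mean, b = 0.4 |
|---|---|---|---|
| None (k = 1) | 70% | -0.25 | -0.49 |
| k = 2 | 49% to 50% | -0.50 | -0.93 |
| Hazard halves (k = 2.5) | 41% to 42% | -0.61 | -1.14 |
| Hazard constant (k = 4) | 25% to 27% | -0.97 | -1.70 |

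The true mean change is zero in every cell.

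**4. A simpler illustration.** If completers average -2 and the others would have averaged 0, the all-patient mean is -2 × the retained share: -1.4 at 70%, -1.0 at 50% and -0.48 at 24%.

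**The case against.** The best defence is that the 12-month endpoint is secondary and carries no formal hypothesis, and that CE marking rests on the 3-month report (sections 6.1 and 10.4). This stands, and it makes any 12-month power calculation moot because no test is set. It does not rescue the wording: an objective without a hypothesis should not be one to demonstrate.

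A reader might also infer more than the documents support:

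- **That about a quarter of patients would carry the 12-month result.** This takes 30% loss in each of four periods. The 30% applies only to month 3. The 36 are described as successfully treated, so it may include failed procedures, an early loss that would not recur. The range is 15% to 70%.
- **That those remaining are the best survivors.** Loss also comes from withdrawn consent and loss to follow-up, which need not relate to pain. Selected completers is as far as the text goes.
- **That patients who progress or need re-ablation are always withdrawn, or that a completer mean is prescribed.** Section 6.5.2 is permissive, and progression counts only where it prevents compliance. The plan is silent on who enters the mean. A completer mean is what results if nothing is added.
- **That a clinically relevant reduction would appear when there is none.** The largest value above, -1.7, is below the 2-point minimally important difference in section 10.2.

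Finally, a composite responder rate is one estimand among several. It counts cancer deaths and consent withdrawals as pain failures. That objection is fair, and it is why the composite should stand beside the mean change and not replace it.

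**Conclusion.** The point holds as a mismatch between objective and analysis. The plan sets out to demonstrate 12-month pain reduction but has no hypothesis for it and no rule for death, withdrawal, progression or re-treatment. Followed as written, it gives a mean in selected completers that cannot support that objective.

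The size is uncertain. With 0% to 40% assumed loss per later 3-month period, 36 down to 8 patients remain. With the assumed link between pain and loss, the spurious mean runs from about -0.25 to -0.5 points at 70% retained, through -0.5 to -0.9 at about 50%, to -1.0 to -1.7 at about 25%. These values are substantial but below 2 points, and the strength of the link has no source in the documents. The gap in the rules is a matter of record and does not depend on these assumptions.

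This should be changed. The endpoint is secondary, but the claim would appear in the final report.

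**What to change.** 1. In section 4.2 and the synopsis, change demonstrate to describe for the 12-month pain objective, consistent with the absence of a formal hypothesis.
2. In sections 5.2 and 10.4, label the 12-month mean change as a summary in patients alive and under observation. Show beside it the numbers dead, withdrawn, re-treated and assessed.
3. Also report, for all treated patients, the proportion alive, without a second ablation and in response at 12 months, with an exact 95% CI. Count death, withdrawal and re-treatment as non-response. Section 6.4.4 defines the Table 4 response only at 3 months, so state that the definition is extended to 12 months.

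This changes the analysis and wording only, not the withdrawal criteria. Table 3 already schedules BPI and pain medication at 12 months, so no new data are needed. The cost is a less favourable 12-month figure and a composite that mixes survival with pain relief.

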5. ENDPOINTS

5.1. Primary Endpoints

The primary endpoints of the study are:

- Change of Worst Pain Score expressed as average reduction of 2 BPI (Brief Pain Inventory) scores: Thoracic/Lumbar/ Peri-acetabulum/Iliac Crest/Sacrum RF Ablation [Time Frame: Baseline vs. 3 months];

Change in pain will be calculated as:

$$\mu c = \text{worst-pain 3-month} - \text{worst-pain baseline}$$

A negative average value for change in pain represents a lowering of the subject's pain score (an improvement, or reduction in pain) and a positive value represents an increase in the subject's pain score (a worsening or increase in pain)

Worst pain score at the target treatment site will be collected from the BPI in the past 24 hours.

- Completion (%) of the ablation procedure without device-related adverse events including in particular nerve injury [Timeframe: Post-procedure, 3 months].

5.2. Secondary Endpoints

- Change of Worst Pain Score: Thoracic/Lumbar/ Peri-acetabulum/Iliac Crest/Sacrum RF Ablation [Time Frame: Baseline vs. 1 month and 12 months];

Worst pain score at the target treatment site will be collected from the Brief Pain Inventory (BPI) in the past 24 hours.

- Usability endpoint: Technical success (ability to perform access to treatment site and perform ablation) and procedural success (ability to perform access to treatment site and perform ablation for one or more complete cycles as planned by the physician) without product specialist intervention [Timeframe: Post-procedure];
- Short learning curve endpoint: procedure time, number of procedural errors, number of procedural and technical success for the same surgeon [Time Frame: Post-procedure];

